# 5.4. Electrocardiogram

#### 5.4.1. Absolute Value and Change from Baseline

CFB in Electrocardiogram (ECG) variables will be calculated for each scheduled post-dose visit. The analyses will be the same as described in Section **5.2.1**.

#### 5.4.2. Clinically Notable ECG

The clinically notable QT interval corrected for Fridericia's method (QTcF) are presented in appendix **9.2**. The number and percentage of subjects with potentially post-baseline Clinically Notable Value(CNV) will be summarized by optimized dose group and overall. The denominator includes all subjects with non-CNV baseline and at least one post-baseline assessment (including unscheduled visit) and the numerator is the number of subjects with non-CNV baseline and CNV at post-baseline.

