Prior to conducting any procedures, written Informed Consent must be obtained from the parent or LAR, and, if appropriate, Informed Assent from the subject. Visit 7 of 810P301 or 810P302, Visit 8 for 810P503 and Visit 6 of 810P204 will be Visit 1 of the OLE. Subjects who meet the requirements for study participation will begin titration at Visit 6 of 810P301 or 810P302 studies and at Visit 5 for the 810P204 study to the dose level of [REDACTED]. Subjects who have completed 810P503 study participation will start titration at Visit 7 to the initial dose of [REDACTED] in this study. Subjects will receive instructions and begin the study at their designated dose and will then continue on their optimized dose until the subject discontinues. The SM dose may be adjusted throughout the study upon the Investigator's discretion.

The following procedures will be performed at Baseline or Visit 1:

1. Obtain written informed consent and assent.
2. Perform physical examination
3. Perform 12-lead ECG
4. Confirm Inclusion/Exclusion criteria
5. Record socio-demographic information
6. Record vital signs (Heart Rate (HR), Blood Pressure (BP), temperature, and Respiratory Rate (RR))
7. Record height, weight and BMI
8. Collect blood samples for hematology, chemistry and pharmacogenomic testing (when applicable)
9. Collect urine sample for drug screen
10. Administer Investigator CGI-S
11. Administer Investigator and Caregiver CGI-I
12. Dispense SM
13. Administer Columbia Suicide Severity Rating Scale (C-SSRS)
14. Collect urine sample for pregnancy test (Females of Child Bearing Potential (FOCBP) only) and urinalysis
15. Assess and record concomitant medications
16. Collect and assess adverse events
17. Administer safety scales (Simpson-Angus, Barnes Akathisia, AIMS)

4.2.2 Visit 2

Visit 2 will occur approximately 2 weeks (± 1 week) following Visit 1.

1. Record vital signs (HR, BP, temperature, and RR)
2. Record height, weight and BMI
3. Collect urine sample for pregnancy test (Females of Child Bearing Potential (FOCBP) only)
4. Administer C-SSRS
5. Administer Investigator CGI-S
6. Administer Investigator and Caregiver CGI-I
7. Administer safety scales (Simpson-Angus, Barnes Akathisia, AIMS)

8. Collect and assess adverse events
9. Dispense SM.
10. Assess and record concomitant medications
11. Assess treatment compliance

4.2.3 Visit 3

Visit 3 will occur approximately 2 weeks (± 1 week) following Visit 2 according to the Schedule of Visits and Procedures.

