1. Record vital signs (HR, BP, temperature, and RR)
2. Record height, weight and BMI
3. Collect urine sample for pregnancy test (Females of Child Bearing Potential (FOCBP) only)
4. Administer C-SSRS
5. Administer Investigator CGI-S
6. Administer Investigator and Caregiver CGI-I
7. Administer safety scales (Simpson-Angus, Barnes Akathisia, AIMS)
8. Collect and assess adverse events
9. Dispense SM.
10. Assess and record concomitant medications
11. Assess treatment compliance

4.2.4 Visit 4

Visit 4 will occur approximately 4 weeks (± 1 week) following Visit 3 according to the Schedule of Visits and Procedures.

1. Record vital signs (HR, BP, temperature, and RR)
2. Record height, weight and BMI
3. Collect blood samples for hematology, chemistry and urinalysis
4. Collect urine sample for pregnancy test (Females of Child Bearing Potential (FOCBP) only)
5. Administer C-SSRS
6. Administer Investigator CGI-S
7. Administer Investigator and Caregiver CGI-I
8. Administer safety scales (Simpson-Angus, Barnes Akathisia, AIMS)
9. Collect and assess adverse events
10. Dispense SM.
11. Assess and record concomitant medications
12. Assess treatment compliance

4.2.5 Visit 5

Visit 5 will occur 4 weeks (± 1 week) following Visit 4 according to the Schedule of Visits and Procedures.

1. Perform 12-lead ECG
2. Record vital signs (HR, BP, temperature, and RR)

3. Record height, weight and BMI
4. Collect urine sample for pregnancy test (FOCBP only) and dispense home pregnancy test kit
5. Collect urine sample for drug screen
6. Administer C-SSRS
7. Administer Investigator CGI-S
8. Administer Investigator and Caregiver CGI-I
9. Administer R-MOAS
10. Administer quality life scales (CHQ-PF28, PSI-4-SF or SIPA)
11. Administer safety scales (Simpson-Angus, Barnes Akathisia, AIMS)
12. Collect and assess adverse events
13. Dispense SM.
14. Assess and record concomitant medications
15. Assess treatment compliance

4.2.6 Visit 6

Visit 6 will occur 3 months (± 1 week) following Visit 5 according to the Schedule of Visits and Procedures.

1. Perform physical examination
2. Perform 12-lead ECG
3. Collect urine sample for urinalysis and urine drug screen (all subjects), and pregnancy test (FOCBP only)
4. Dispense home pregnancy test kit
5. Record vital signs (HR, BP, temperature, and RR)
6. Record height, weight and BMI
7. Collect blood for samples for hematology and chemistry
8. Administer C-SSRS
9. Administer Investigator CGI-S
10. Administer Investigator and Caregiver CGI-I

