4.2.8 Visit 25 [(End of Study (EOS)] (Month 60 +/- 2 weeks)

Subjects who complete the study (60 months) will be instructed to down titrate for 2 weeks before returning to the office for the EOS Visit.

This document is confidential. It contains proprietary information of Supernus® Pharmaceuticals, Inc. Any viewing or disclosure of such information that is not authorized in writing by the Sponsor is strictly prohibited. Such information may be used solely for the purpose of reviewing or performing this study.

Subjects may discontinue prior the end of the study if the subject or the LAR withdraws assent and/or consent, or if the Investigator or the Sponsor decide it is no longer in the best interest of the subject. If the decision is made to discontinue early then the subject will be contacted and instructed to down-titrate at least 2 weeks prior to the EOS Visit.

The following procedures will be performed for subjects who complete the study (60 months) or discontinue early.

1. Perform physical examination
2. Perform 12-lead ECG
3. Collect urine sample for urinalysis and urine drug screen (all subjects), and pregnancy test (FOCBP only)
4. Record vital signs (HR, BP, temperature, and RR)
5. Record height, weight and BMI
6. Collect blood samples for hematology and chemistry
7. Administer C-SSRS
8. Administer safety scales (Simpson-Angus, Barnes Akathisia, AIMS)
9. Administer efficacy scales (R-MOAS, CGI-I and CGI-S, only for subjects who discontinue early)
10. Administer quality life scales (CHQ-PF28, PSI-4-SF or SIPA, only for subjects who discontinue early)
11. Collect and assess adverse events
12. Collect SM and assess treatment compliance
13. Assess and record concomitant medications

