5 ANALYSIS VARIABLES

5.1 Safety Variable

The primary outcome measure will be the safety and tolerability of the SM. At every visit, safety assessment will consist of monitoring and recording of all AEs and concomitant medications, clinical laboratory tests, together with prolactin and insulin plasma levels, vital signs, physical examinations and 12-lead ECG and suicidality thoughts and behaviors.

Assessment of possible neurological side effects and EPS will be performed using the Simpson-Angus scale, the Barnes Akathisia scale and the Abnormal Involuntary Movement scale. A positive rating or finding on any safety scale will be captured as an Adverse Event at the discretion of the Investigator if it satisfied the criteria for Adverse Event.

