5.1.7 Physical Examinations and Electrocardiograms (ECGs)

A physical examination and a 12-lead ECG will be obtained at visits designated on the Schedule of Visits and Procedures ([Table 1](#)). Additional ECGs may be performed at other times if deemed necessary by the Investigator.

The ECG will be recorded while the subject is resting in a supine position. The ECG will electronically measure the PR, QRS, QT, and QTc intervals, and heart rate.

All ECG tracings will be reviewed within 24 hours by the Investigator or qualified Sub-Investigator. PR intervals will be determined for each of these ECGs from a single reading. Invalid measurements will be repeated. QTc will be reported as QTcF (QT corrected using Fridericia's method).

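### The QTcF notable-value table in SAP 5.4.2 has no on-treatment condition, so a subject who leaves before Visit 5 can enter the denominator on a post-taper ECG alone

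*SAP*

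**What the plan says.** **The analysis rule.** SAP 5.4.2 sets the denominator as follows: "The denominator includes all subjects with non-CNV baseline and at least one post-baseline assessment (including unscheduled visit". For the cases, "the numerator is the number of subjects with non-CNV baseline and CNV at post-baseline". Neither part mentions treatment status, taper or time since last dose. Baseline is the safety baseline of SAP Table 2, which is Visit 1.

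**The ECG schedule.** Protocol 5.1.7 refers ECG timing to the schedule: "A physical examination and a 12-lead ECG will be obtained at visits designated on the Schedule of Visits and Procedures". Table 1 and SAP Appendix 9.1 mark an ECG at Visit 1, Visits 5 to 24 and Visit 25 (EOS). The procedure lists agree. The item "Perform 12-lead ECG" appears at Visit 1 and from Visit 5 on, and is absent from Protocol 4.2.2 to 4.2.4 (Visits 2, 3 and 4). On timing, Protocol 4.2.5 says "Visit 5 will occur 4 weeks (± 1 week) following Visit 4 according to the Schedule of Visits and Procedures".

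**Early leavers.** Protocol 4.2.8 says that after a decision to stop early "the subject will be contacted and instructed to down-titrate at least 2 weeks prior to the EOS Visit". Protocol 3.2.5 and 4.6 also prescribe a taper of about 2 weeks, and 4.6 places it before EOS. The EOS procedures include an ECG.

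**Qualifying text.** Protocol 5.1.7 lets the Investigator add ECGs when needed, and SAP 5.4.2 counts unscheduled visits. Protocol 5.1 begins "At every visit, safety assessment will consist of monitoring and recording of all AEs and concomitant medications, clinical laboratory tests" and its list goes on to "vital signs, physical examinations and 12-lead ECG and suicidality thoughts and behaviors", which does not match Table 1.

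**The concern.** Safety is the primary objective, and this is the SAP's only table of QTcF threshold crossings. Read with the visit schedule, the denominator rule mixes two kinds of subject: those with at least one ECG at their treatment dose after Visit 1, and those whose only later ECG was taken after a taper. If a QTcF effect depends on current dose, the second group adds to the denominator and little or nothing to the numerator, so the percentage drifts down. That group consists of people who stopped during dose adjustment or shortly after it, including any who stopped for adverse events. A reader of the table could not see how many there were.

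**Working it through.** **1. When is the first scheduled post-baseline ECG?** The intervals in Protocol 4.2.2 to 4.2.5 are 2, 2, 4 and 4 weeks, each ±1 week.
- Nominal: 2 + 2 + 4 + 4 = 12 weeks
- Earliest: 1 + 1 + 3 + 3 = 8 weeks
- Latest: 3 + 3 + 5 + 5 = 16 weeks

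The gap therefore runs past the last optimization visit (Visit 4, nominal Week 8) to anyone who leaves before Visit 5.

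**2. What does the rule do with a subject who leaves in that gap?** All have a non-notable baseline.

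| Subject leaves before Visit 5 and… | In denominator? | ECG at treatment dose after Visit 1? |
|---|---|---|
| returns for EOS after taper, no unscheduled ECG | yes | no |
| had an unscheduled ECG before taper | yes | yes |
| does not return, no unscheduled ECG | no | no |

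Only the first row is the problem. Subjects who reach Visit 5 and have that ECG while on treatment are unaffected, because they belong in the denominator in any case.

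**3. Effect on the reported rate.** Let p be the rate of notable values among subjects with an on-treatment ECG, q the rate among subjects with only a post-taper ECG, and d the latter's share of the denominator.

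Reported rate = p(1 − d) + q·d

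With q = 0 this is p(1 − d), a relative loss of d. With q above zero but below p, the relative loss is d(1 − q/p). With q = p there is none.

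**4. Numbers.** The plan states no expected QTcF rate and no early-dropout share, so there is no figure of its own to reproduce. All values of p, q and d below are assumptions.

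| d | subjects, if the denominator is 600 | p = 3.0%, q = 0 reads as |
|---|---|---|
| 5% | 30 | 3.0 × 0.95 = 2.85% |
| 10% | 60 | 3.0 × 0.90 = 2.7% |
| 20% | 120 | 3.0 × 0.80 = 2.4% |

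If q is half of p, the loss halves: at d = 10%, 3.0 × 0.9 + 1.5 × 0.1 = 2.85%. The 600 is the planned enrolment; the actual denominator would be smaller.

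**5. If no cases are seen.** The one-sided 95% upper bound is 1 − 0.05^(1/n). On 600 it is 0.50%. On the 570, 540 or 480 subjects who would have an on-treatment ECG at d = 5%, 10% or 20%, it is 0.52%, 0.55% or 0.62%.

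**6. Is there an anchor for d?** The nearest figure is in Protocol 1.3: 7 of 78 subjects (7/78 = 9.0%) in the Phase 2 extension, 810P203, stopped for adverse events. It covers one reason for stopping and up to 6 months of treatment. The quantity d needs all reasons, only the time before Visit 5, a returned EOS visit and no unscheduled ECG. The 9.0% neither estimates nor bounds it.

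**7. Change-from-baseline rows.** Appendix 9.2 also lists QTcF change categories. Subjects who completed a parent study were converted to the starting dose before Visit 1, so their baseline is generally on drug. A post-taper ECG is then compared with an on-drug baseline, which makes a large increase still less likely to appear.

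**The case against.** **Any post-baseline assessment is a common safety denominator, and the SAP does not call these subjects non-cases.** Both are true. A reader might infer that early leavers are classed as non-cases, or cannot become cases. The numerator takes any post-baseline notable value, so a notable EOS or unscheduled ECG makes an early leaver a case. Non-case is the likely outcome of a post-taper ECG, not a rule.

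**Not every early leaver is affected.** A reader might infer that everyone who leaves during optimization has only an off-drug ECG. The documents do not support that. Unscheduled ECGs are allowed and counted, and people stopping for adverse events are plausible candidates for one. Those with no later ECG are not in the denominator. No interval between last taper dose and EOS is given, so post-taper is as far as the text goes. These points shrink the affected group. They do not remove it, because extra ECGs are discretionary.

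**Restricting the denominator does not recover the missing data.** This stands. The corrected rate describes subjects who had an on-treatment ECG, and early leavers may have had a different risk.

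**Other ECG summaries exist.** Protocol 6.8.4 tabulates overall ECG findings, and SAP 5.4.1 summarizes change by visit. They limit the consequence, but neither is the QTcF threshold table.

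**The low-dose column.** SAP 3.1 groups subjects who leave before maintenance by their EOS dose. A reader might infer that they pile up in the lowest dose group. That would follow only if EOS dose means a taper dose, which the SAP does not say.

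**The every-visit sentence.** A reader might infer from Protocol 5.1 that ECGs are required at Visits 2 to 4. The ECG section, 5.1.7, defers to Table 1. The same sentence also lists laboratory tests and physical examinations, which Table 1 does not place at every visit either. This is a separate, minor inconsistency.

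**Conclusion.** The point holds in a limited form. SAP 5.4.2 lacks an on-treatment condition, and under the schedule that Table 1, the visit lists and SAP Appendix 9.1 share, a lone post-taper ECG can qualify a subject for the QTcF denominator. This tends to understate on-treatment incidence. The relative size equals the share of such subjects if post-taper ECGs yield no cases, and is smaller if they yield some. Step 3 also takes p as the rate among subjects who do have an on-treatment ECG; it says nothing about the unobserved risk in early leavers. Because the documents do not give the share, no size can be claimed. The direction and mechanism are established; the percentages are illustrations. The change is worth making because it is cheap and the table serves the primary objective.

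**What to change.** **In SAP 5.4.2:**
- Apply an on-treatment condition to both numerator and denominator: ECGs after Visit 1, scheduled or unscheduled, excluding post-taper EOS ECGs.
- Identify post-taper EOS ECGs by the EOS visit label together with the last-dose date, which SAP 4.6 already needs for exposure. Use the taper-start date instead if it is collected; the documents do not show that it is. State in advance how an unscheduled ECG dated during taper is classed.
- Report, by dose group and overall, the number of subjects with no on-treatment ECG.
- Show post-taper EOS ECGs, including any notable values, in a separate row, so that no case disappears.
- State which Appendix 9.2 rows count as notable, since the lowest categories (≤450 ms, and a change ≤30 ms) are listed with the rest. Reconcile SAP 3.4, which excludes unscheduled data from summaries, with 5.4.2, which counts it.

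**In the protocol:** reconcile the every-visit wording of 5.1 with 5.1.7, Table 1 and 4.2.2 to 4.2.4. Which ECG schedule is right is not a matter for this review.

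**Cost:** SAP wording, one derivation flag, one extra table row and a protocol clarification. The denominator becomes smaller and the rate probably slightly less favourable, and that rate describes only subjects with an on-treatment ECG.

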# 5.5. Physical Examination

Data listing will be provided.

# 5.6. Extrapyramidal Symptoms (EPS)

Absolute value and CFB of each item in each of EPS scales will be analyzed descriptively at each scheduled visit by the optimized dose group and overall. Data listings will be provided.

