5.1.4 Management of Treatment-Emergent EPS

If a subject experiences treatment-emergent EPS (including akathisia, dystonia, Parkinsonism, or tardive dyskinesia), benztropine will be permitted at a starting dose of 0.5 mg BID up to a range of 1 to 4 mg/day. Lorazepam (1 to 2 mg per dose not to exceed three times daily) and clonazepam (0.25 to 1 mg per dose not to exceed twice daily) will also be permitted to treat the occurrence of extrapyramidal symptoms.

For the treatment of Akathisia, propranolol is recommended up to 90 mg /day in divided doses, three times per day, starting at 10 mg BID and up to 30 mg TID, as needed.

A positive finding on an EPS safety assessment scale (Barnes Akathisia, Simpson-Angus, AIMS) does not necessarily equate to an EPS event. Investigators should evaluate positive findings on the EPS safety assessment scales and integrate them into a global clinical observation to determine if an AE of EPS should be recorded.

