6.8 Safety Analysis

Evaluation of safety will be performed for the safety population. Safety data that will be evaluated include concomitant medications, AEs, clinical laboratory results, vital signs, ECGs, and findings from the physical examinations. The occurrence of neurological side effects will be assessed by looking at any worsening in scores from Baseline (Visit 1) to each subsequent visit for each of the Simpson-Angus scale, Barnes Akathisia scale, and AIMS. Suicidal ideation and suicidal behavior will be measured by C-SSRS.

All summary tables related to safety analyses will use the safety population.

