6.8.8 Extrapyramidal Symptoms

The occurrence of neurological side effects will be assessed by looking at the changes in scores from Baseline to each of the post-Baseline visit for each of the Simpson-Angus scale, Barnes Akathisia scale, and AIMS. For each item on each of these scales, the number (and percentage) of subjects with a worse score at any post-Baseline visit, compared to Baseline, will be presented. A listing of these subjects will also be provided.

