#### **1. OBJECTIVES AND ENDPOINTS**

The objectives and endpoints are listed in Table 1.

rusie it objectives and Enapoints					
Objectives	Endpoints				
Safety Objective (Primary): Long-term safety on the use of SPN-810 as a treatment for impulsive aggression (IA) in subjects (6-17 years of age) with Attention Deficit/Hyperactivity Disorder (ADHD) when taken in conjunction with standard ADHD treatment only after satisfactory participation in a preceding double- blind study (810P301, 810P302,	
 
Endpoints         
 
Adverse Events
 
Extrapyramidal Symptoms (EPS) scales (Simpson-Angus Scale, Barnes Akathisia Scale, and Abnormal Involuntary Movement Scale)
 
Clinical Laboratory Tests (Hematology, Chemistry, Insulin, Prolactin and Urinalysis)
 
Concomitant Medications
 
Vital signs, Standardized BMI, Physical Examination and ECG (12- lead)
 
Columbia Suicide Severity Rating Scale (C-SSRS)
 
 
 
				
810P503 or 810P204). Efficacy Objective (Secondary): Long-term efficacy on the use of SPN-810 as a treatment for impulsive aggression (IA) in subjects (6-17 years of age) with ADHD when taken in conjunction with standard ADHD treatment.	
 
Change from Baseline (CFB) in Retrospective-Modified Overt Aggression Scale (R-MOAS) at each scheduled visit
 
Clinical Global Impression – Improvement Scale (CGI-I) at each scheduled visit
 
CFB in Clinical Global Impression – Severity Scale (CGI-S) at each scheduled visit
 
				
Quality of Life Objective (Exploratory): Long-term quality of life on the use of SPN-810 as a treatment for impulsive aggression (IA) in subjects (6-17 years of age) with ADHD when taken in conjunction with standard ADHD treatment.	
 
CFB in Child Health Questionnaire Parent Form 28-item (CHQ- PF28) at each scheduled visit
 
CFB in Parenting Stress Index – Short Form (PSI-4-SF) or Stress Index for Parents of Adolescents (SIPA) at each scheduled visit
 
Socio-demographics Characteristics
 
				

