# 3. GENERAL CONSIDERATIONS FOR DATA ANALYSES AND HANDLING

#### 3.1. General Statistical Methods

All statistical analysis will be performed using SAS version 9.4 or higher.

All data summaries will be presented by the optimized dose group (<18 mg/day; 18-<24 mg/day, 24-<36 mg/day or 36-54 mg/day) and overall. The optimized dose is defined as the first maintenance dose (at visit 5) for subjects entering maintenance period; otherwise using the end of study (EOS) dose for subjects discontinued prior to maintenance period.

Continuous variables will be summarized descriptively using number of subjects (n), mean, standard deviation (SD), median, minimum, and maximum.

Categorical variables will be summarized descriptively using counts and percentages. However, the number of patients with missing data will be excluded from the denominator for the percentage calculation. When the denominator for the percentage is different from the number of subjects in the treatment column header, the denominator will be clearly specified in the table or in a footnote for the table.

Individual subject data will be listed by subject ID. Unscheduled measurements (unless defined as baseline) will be excluded from summary tables but will be included in data listings. For assessments that are repeated or unscheduled, unless otherwise specified, the non-missing values from the first assessment will be used for generating summary statistics.

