- Number and Percent of subjects with Treatment-Emergent Adverse Events Leading to Withdrawal of Study Medication by System Organ Class and Preferred Term
- Number and Percent of Subjects with Treatment-Emergent Adverse Events of special interest by System Organ Class and Preferred Term *Note: Adverse events of special interest (AESI) are collected and flagged on eCRF.*
- Listing of Deaths

A data listing of death will be provided. If no death occurred, a blank listing with "No subject died on this study." will be presented.

Listing will be provided for AEs.

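### SAP 5.6 drops, without declaring it, the protocol's per-item count of subjects who ever worsen on the EPS scales

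*SAP*

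**What the plan says.** Protocol 6.8.8 sets out two analyses of the Simpson-Angus, Barnes Akathisia and AIMS scales. The first is the change in score from Baseline to each post-Baseline visit. The second is at subject level: for each item on each scale, "the number (and percentage) of subjects with a worse score at any post-Baseline visit, compared to Baseline, will be presented", followed by a listing of those subjects. Protocol 6.8 describes the neurological assessment in the same terms, as "any worsening in scores from Baseline (Visit 1) to each subsequent visit".

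SAP 1 places these scales under the primary safety objective: "Extrapyramidal Symptoms (EPS) scales (Simpson-Angus Scale, Barnes Akathisia Scale, and Abnormal Involuntary Movement Scale"). SAP 5.6 then specifies that "Absolute value and CFB of each item in each of EPS scales will be analyzed descriptively at each scheduled visit", by optimized dose group and overall, and adds data listings. SAP 5.6.1 to 5.6.3 only describe the three instruments. The SAP's table of contents shows no other EPS section. SAP 8 reports one departure from the protocol: compliance is calculated in mg instead of tablets.

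**The concern.** The SAP keeps the first protocol analysis and leaves out the second, with no reason given and no entry in SAP 8. The missing table is the only subject-level frequency that the protocol planned from these scales. Protocol 1.5 names the frequency of extrapyramidal symptoms among the primary outcome measures.

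By-visit summaries answer a different question. They describe each visit separately and do not link subjects across visits. A few subjects with lasting worsening and many subjects with brief worsening can therefore look the same. For a long-term safety study of up to 60 months, the difference matters to anyone reading the EPS results. If the SAP is followed as written, a result that the protocol promised on a primary safety endpoint will not be tabulated.

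**Working it through.** **Step 1: compare the texts.**

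| Element | Protocol 6.8.8 | SAP 5.6 |
|---|---|---|
| Change from baseline at each visit | Yes | Yes, by item |
| Per item, n (%) worse at any post-baseline visit | Yes | No |
| Listing of the subjects who worsened | Yes | General data listings only |
| Omission declared in SAP 8 | – | No |

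**Step 2: can another planned output supply the count?**

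- *By-visit summaries.* SAP 3.1 says: "Continuous variables will be summarized descriptively using number of subjects (n), mean, standard deviation (SD), median, minimum, and maximum". The maximum shows that someone worsened at a visit. It does not show how many different subjects worsened over the study. Treating items as categorical would give the number worse at each visit, but still not the number ever worse.
- *Adverse events.* SAP 5.1 plans "Number and Percent of Subjects with Treatment-Emergent Adverse Events of special interest by System Organ Class and Preferred Term". That table counts events reported by the investigator. Protocol 5.1.4 says that a positive finding on an EPS scale "does not necessarily equate to an EPS event", so the two counts differ by design.
- *Unscheduled ratings.* SAP 3.1 and 3.4 keep these out of summary tables. Worsening seen only at an unscheduled visit would appear only in a listing.

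**Step 3: how far can the by-visit tables leave the answer open?** The documents give no per-item worsening rate, so the rates below are assumed and the result is a bound, not a forecast.

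Inputs:
- N = 600, the approximate planned enrolment (Protocol 4.1).
- V = 24 post-baseline visits, Visits 2 to 25, with the scales rated at every visit (Protocol Table 1).
- w = assumed fraction worse on an item at each visit.
- No dropout.

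If the same subjects are worse at every visit, the proportion ever worse is w. If different subjects are worse each time, it is min(1, V × w).

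| V | w | Lower bound | Upper bound |
|---|---|---|---|
| 24 | 0.5% | 0.5% (3 of 600) | 24 × 0.5% = 12% (72) |
| 24 | 1% | 1% (6) | 24 × 1% = 24% (144) |
| 24 | 2% | 2% (12) | 24 × 2% = 48% (288) |
| 5 (Visits 2–6) | 1% | 1% (6) | 5 × 1% = 5% (30) |

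**Step 4: confirm that the summaries coincide.** Take w = 1% and a worsening of one point, with everyone else unchanged. At every visit, in both extreme cases:

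- n = 600
- mean change = 6/600 = 0.01
- SD = √[(600/599) × 0.01 × 0.99] = 0.0996
- median 0, minimum 0, maximum 1

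The overall change-from-baseline summaries are identical, yet 6/600 are ever worse in one case and 144/600 in the other. For the tables by dose group to coincide too, the number worse per visit in each group must match. The bound itself applies within each group in the same way.

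**The case against.** The strongest reply accepts the omission and disputes its weight.

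- *The illustration is extreme.* The rates are assumed. Twenty-four visits is the maximum for 60 months, participation is renewed every six months, and many subjects will have fewer ratings. The upper bound also requires every worsening to resolve by the next visit and never recur in the same subject. This stands. The 24% and 48% figures show only that the by-visit tables do not determine the answer. The five-visit range of 1% to 5% is the less extreme case.
- *EPS frequency is still estimated.* Treatment-emergent EPS are reported as events of special interest and tabulated per subject, and a one-point rise on one item is not an EPS event. This is correct, and it confines the gap to scale-based worsening. It does not replace the scale-based count, because the protocol keeps the two measures distinct.
- *The count can be derived from the listings.* This is true, but it would then be an unplanned derivation, with the denominator and the handling of unscheduled ratings chosen after the data are seen.
- *The fix adds rules that the protocol does not state.* This is partly right. Protocol 6.8.8 gives only the per-item n (%) and the listing. The dose-group split follows SAP 3.1, but the denominator and the unscheduled-visit rule are proposals. Counting unscheduled ratings would be an exception to SAP 3.1 and 3.4.

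**Conclusion.** The concern holds and should be fixed. It rests on the comparison of texts, not on the illustration: a protocol-specified subject-level analysis of a primary safety endpoint is missing from the SAP and its removal is not declared. No planned output gives the same result.

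The numerical effect on this study cannot be stated, because no per-item worsening rate is documented. Under the assumptions shown, 1% worse per visit is compatible with 1% to 24% ever worse over 24 visits, or 1% to 5% over five. EPS recorded as adverse events are still counted, and the item data will be listed, so the information is not lost. It is not a planned result.

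**What to change.** In SAP 5.6, keep the by-visit summaries and add:

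1. For each item of the three scales, n (%) of subjects with a score worse than the safety baseline at any post-baseline visit, by optimized dose group and overall.
2. A denominator: subjects with a baseline rating and at least one post-baseline rating.
3. A rule for unscheduled ratings. Counting them fits the protocol's reference to any post-Baseline visit. SAP 5.4.2 already does so for QTcF, where the denominator requires "at least one post-baseline assessment (including unscheduled visit"). State this as an exception to SAP 3.1 and 3.4.
4. The protocol's listing of the subjects who worsened.

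If the table is deliberately not wanted, say so in SAP 8 and give the reason. Counts on scale totals or global scores, and rates per 100 patient-years, are optional extras.

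The cost is one SAP paragraph, one table per scale and one listing, all from data already collected. Study conduct does not change.
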